### **Habitual Dietary Intake**

Three dietary recalls will be administered (two weekdays and one weekend) using Automated Self-Administered 24-h dietary recall (ASA-24). The ASA-24 is based on the validated Multiple Pass Method (38) and has been validated against standardized interviewer-administered 24-hr recalls (39). Children with Parent/Guardian supervision will report all food and beverage consumed during the previous day (midnight to midnight). The ASA-24 uses the USDA's Food and Nutrient Database for Dietary Studies to calculate dietary intake and HEI scores (40), which is composed of a thirteen component scoring system adhering to the 2015-2020 Dietary Guidelines for Americans.

Participants will have a 24-hour dietary recall during the HF challenge to assess food intake the previous day.

**PROTOCOL TITLE:** Metabolic Response to a High-Fat Challenge in Children and Adolescents.  
**High-fat Challenge**

[figure not shown]
The HF-challenge will be started between 7:00 AM and 10:00 AM. To increase the comfort level of the participants, a topical anesthetic will be applied to numb the location of the needle. An intravenous catheter will be placed, and blood drawn prior the consumption of the shake (baseline). A liquid HF shake will be consumed over a 10-minute period. Participants will be highly encouraged to consume the entire shake; however, pre- and post-weight of the shake will be taken if entire shake isn't consumed. The shake will be composed of a mixture of BOOST Glucose Control® (Nestlé Products) supplemented with

	BOOST Glucose Control®	Palm oil	Total
Energy (kcal)	190	240	430
Protein (g)	16	0	16
Carbohydrates (g)	16	0	16
Fat (g)	7	28	35
SFA (g)	1	14	15
MUFA (g)	5	10	15
PUFA (g)	1	4	5

**Table 1.** Nutrient composition of an 8oz portion of the HF liquid shake composed of a mixture of BOOST Glucose Control® and palm oil.

palm oil. Palm oil contains approximately 50% saturated fatty acids (palmitic acid [FA 16:0] and stearic acid [FA 18:0]) and 40% monounsaturated fatty acids (oleic acid [FA 18:1]). Each participant will consume a volume of liquid equivalent to 25% of their estimated daily caloric needs, calculated by the USDA Dietary Reference Intakes using a moderate activity factor. Maximum volume of the HF shake will contain 54 grams of fatty acids. Blood samples will be taken at 30, 60, 120, and 180 minutes. A maximum volume of 46 mL of blood (approximately 4 tablespoons) will be collected from each participant during the 3-hour meal challenge. The total blood amount accounts for 1mL of 'flush blood' at each timepoint, to account for the small amount of blood left in the line and flushed out with saline between draws.

[figure not shown]
**Figure 1.** Sample collection timeline.

**Figure 2.** Sample collection details.

## PROTOCOL TITLE: Metabolic Response to a High-Fat Challenge in Children and Adolescents.

### Office of Research Operations - Plasma samples (2.0 mL K2 EDTA tubes)

Collection Timepoints: baseline (pre-shake, fasting), 30 minutes, 60 minutes, 120 minutes, and 180 minutes

#### Sample Collection details:

Amount blood drawn: 2.0 mL

#### CRU Post-Sample Collection:

1. Following venipuncture, invert the collection tube 10x
2. Transfer collection tube on ice.

CRU Staff will transport sample to ORO Lab (Borwell 7) after each blood draw

#### ORO Sample Processing:

1. Centrifuge: 2000g for 10 minutes at room temperature. No brake.
2. Extract plasma. Aliquot 200µL. Evenly distribute remainder of plasma.
3. Store at -80C in 2mL screw top cryovials with 0.5mL inserts.

The CRC for the High-Fat Challenge will label all plasma storage tubes. Nomenclature is: Subject ID\_Timepoint\_Sample type\_date

PROTOCOL TITLE: Metabolic Response to a High-Fat Challenge in Children and Adolescents.

Eventual shipping for Metabolomics:

Attn: [name]  
University of Michigan  
Metabolomics Core  
[name]  
[name]  
[name]

Shipping conditions:

Samples should be shipped frozen, in a secondary container, on dry ice. Tubes should be clearly labeled with sample identifiers (described in the Sample Submission Form) and include a hard copy of the Sample Submission Form with the shipment

**Center of Molecular Epidemiology – RNA extraction (2.5 mL PAXgene tubes)**

Collection Timepoints: baseline (pre-shake, fasting), 30 minutes, 60 minutes, 120 minutes, and 180 minutes

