## 2.0 Objectives\*

Cardiorespiratory fitness (CRF) in youth is an independent risk factor for type 2 diabetes (T2D) (1) and cardiovascular disease (CVD) (2), and in adulthood, CRF is inversely associated with mortality (3). Only 40% of youth in the United States have a healthy CRF (4), possibly influenced by increased sedentary time (5), decreased moderate-to-vigorous activity (5), increased obesity (6), and lower dietary quality (7). CRF is estimated by measuring maximum oxygen consumption ( $\text{VO}_2\text{max}$ ) during intense exercise, challenging the capacity of the respiratory and circulatory systems to supply oxygen to the skeletal muscles for generation of ATP. CRF is directly related to mitochondrial respiratory capacity and is associated with fatty acid (FA) oxidation (8, 9). Profiling the response of the FA oxidation intermediates, measured by metabolomics, and FA oxidation gene expression, measured within peripheral blood mononuclear cells (PBMC), to a high-fat (HF) challenge may provide a mechanistic link between CRF and risk for T2D and CVD. The primary objective of this study is to challenge mitochondrial FA oxidation via administering a HF meal, assessing the relationship between FA oxidation and CRF in youth (age 8-17 years). *We hypothesize that low CRF will be associated with inefficient mitochondrial beta-oxidation, profiled by medium-chain acylcarnitines (AC), and increased extra-mitochondrial oxidation, profiled by dicarboxylic FA (FA-COOH).* The secondary objective of this study is to assess the relationship between FA oxidation intermediates and measures of insulin resistance (IR), glucose homeostasis, and cardiometabolic risk. *We hypothesize that incomplete mitochondrial beta-oxidation and increased extra-mitochondrial oxidation will mediate the relationship between CRF with metabolic health.* We will test our hypotheses through these aims:

[figure not shown]

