**SPECIFIC AIM 1. Determine if CRF is associated with modifiable behaviors including body composition, daily physical activity (PA), and habitual dietary intake.** Children, aged 8-17 years (body mass index (BMI) percentile  $\geq 85\%$  for sex/age, matched with leans [ $5\% \leq \text{BMI percentile} < 85\%$ ],  $n=50$ ), will be recruited. Gold-standard stress testing will use a modified Bruce multistage protocol, increasing both the elevation and speed over time, to measure  $\text{VO}_2\text{max}$ . Body composition will be measured using bioelectrical impedance (Seca, Hamburg, Germany). Over seven days, participants will be asked to wear an ActiGraph accelerometer (ActiGraph, Pensacola, FL) and complete three dietary recalls using Automated Self-Administered 24-h dietary recall (ASA-24). We will assess the interaction between PA and habitual dietary intake, measured by the Healthy Eating Index (HEI) score (10), with  $\text{VO}_2\text{max}$ . We will consider if the interaction between PA and HEI score modifies the linear association between percent fat mass and  $\text{VO}_2\text{max}$ .

**SPECIFIC AIM 2. Following a HF-challenge, assess the relationship between mitochondrial and extra-mitochondrial FA oxidation with CRF.** After an overnight fast, participants will consume the HF-challenge, composed of palm oil supplemented Boost® (15% kcal carbohydrates, 15% kcal protein, 70% kcal lipid). Blood will be sampled via intravenous line at baseline ( $t_0$ ) and after consuming the challenge ( $t_{30}$ ,  $t_{60}$ ,  $t_{120}$ , and  $t_{180}$  minutes) and analyzed for fluctuations in glucose and insulin. Plasma targeted metabolomics will be conducted, profiling AC and FA-COOH metabolites. PBMC will be isolated and mRNA levels of genes related to beta- and omega-oxidation will be determined by qPCR. Fold change calculations and longitudinal trajectories, measured by empirical Bayes time-series analysis (11), will quantify the response of metabolites and expression of genes to the challenge. Mixed

PROTOCOL TITLE: Metabolic Response to a High-Fat Challenge in Children and Adolescents. regression models will determine the association between CRF with FA oxidation metabolite and gene (1) absolute levels, (2) longitudinal trajectories, and (3) ratios (12), considering the influence of age, sex, pubertal status, and BMI percentile.

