To sustain exercise, oxygen is circulated to skeletal muscles to be utilized within the mitochondrial via the electron transport chain, supporting the creation of ATP (reference). Therefore, CRF serves as a measurement of mitochondrial respiratory capacity and has been associated with FA oxidation (8, 9). In rats selectively bred for high running capacity (9), Overmyer et al. demonstrated that CRF is associated with a more rapid mitochondrial protein deacetylation at the initiation of exercise and a more efficient and prolonged oxidation of FA during exercise. The inability to efficiently metabolize FAs is associated with elevated levels of bioactive lipids, such as ceramides and diacylglycerols (DG), which leads to cellular stress, inflammation, and increased risk of T2D and CVD (21). The second objective of this grant proposal is to challenge mitochondrial FA oxidation via administering an acute HF meal, assessing the relationship between FA oxidation and CRF (**Specific Aim 2**). Mitochondria are the central hub of FA oxidation (beta-oxidation); however, the endoplasmic reticulum (omega-oxidation) and peroxisomes (alpha-oxidation) serve as FA oxidation rescue pathways when beta-oxidation is overloaded (22). Using plasma metabolomics during the meal challenge, we hypothesize that low CRF will be associated with inefficient mitochondrial beta-oxidation, profiled by AC, and increased extra-mitochondrial oxidation, profiled by FA-COOH (22, 23). Beta- and omega-oxidation gene expression will be quantified within PBMC; a cell type frequently used in human challenges due to its accessibility and expression being comparable to skeletal muscle tissue (24). There have been no studies to date that have used an acute nutrient challenge to assess the relationship between FA oxidation and CRF. Morris et al. assessed variation in the lipidome in response to an oral lipid tolerance test (OLTT) in healthy adults (n=40) observing differences in production of phosphatidylcholines (PC), sphingomyelins (SM)

PROTOCOL TITLE: Metabolic Response to a High-Fat Challenge in Children and Adolescents. and ceramides related to CRF (25). Profiling FA oxidation intermediates and PBMC gene expression rather than the lipidome will provide a more direct readout of FA efficiency.

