## 4.0 Study Endpoints\*

PROTOCOL TITLE: Metabolic Response to a High-Fat Challenge in Children and Adolescents.

Variable	Instrument / Measurement	Source	Time Series (minutes)				
			0	30	60	120	180
Aim 1: Cardiorespiratory fitness with modifiable behaviors							
Demographics	Questionnaires	Participant self-report	X				
Anthropometrics	Weight, height, BMI percentile, waist circumference, blood pressure, and BIA results	RA	X				
Dietary recall	ASA-24	Participant self-report	X				
Cardiorespiratory fitness	Maximal oxidative capacity treadmill test	Sports cardiology	X				
Physical activity	Actigraph	actigraph	X				
Aim 2: HF-challenge response with cardiorespiratory fitness							
Metabolic response	Untargeted metabolomics and PBMC gene expression	blood	X	X	X	X	X
Cardiorespiratory fitness	Maximal oxidative capacity treadmill test	Sports cardiology	X				
Aim 3: HF-challenge response with metabolic health							
Metabolic response	Untargeted metabolomics and PBMC gene expression	blood	X	X	X	X	X
Fasting laboratory measures	HbA1C, IGF-1, C-peptide, lipid panel	blood	X				
Response laboratory measures	glucose, insulin	blood	X	X	X	X	X

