**Sample Collection details:**

Amount blood drawn: 2.5 mL

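### The gene-expression endpoint is specified in isolated PBMC, but the documented RNA workflow is a PAXgene tube with no cell-separation step

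*Combined protocol and SAP*

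**What the plan says.** Four places tie the endpoint to one cell type.

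- Section 2.0, opening paragraph: "FA oxidation gene expression, measured within peripheral blood mononuclear cells (PBMC".
- Section 2.0, Specific Aim 2: "PBMC will be isolated and mRNA levels of genes related to beta- and omega-oxidation will be determined by qPCR".
- Section 3.0: "gene expression will be quantified within PBMC; a cell type frequently used in human challenges". The choice is justified there by accessibility and by "expression being comparable to skeletal muscle tissue (24".
- Section 4.0 endpoint table: "Untargeted metabolomics and PBMC gene expression", under both Aim 2 and Aim 3, at all five timepoints.

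Section 6.0 describes something else. The RNA block is headed "RNA extraction (2.5 mL PAXgene tubes", with "Amount blood drawn: 2.5 mL" at each timepoint. The tube is inverted, kept at room temperature and taken to the laboratory after the visit. The Genetic Analysis paragraph then goes straight to RNA isolation and PCR. The EDTA research tube is centrifuged and its plasma aliquoted ("Evenly distribute remainder of plasma"), with no instruction to keep or process cells. The other listed tubes go to Pathology for HbA1c, glucose with lipids, and insulin.

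No blood count or differential is listed. The adjustment variables named for Aims 2 and 3 are BMI percentile, puberty, sex and age.

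**The concern.** Staff who follow the collection instructions will not produce the specimen that the endpoint names. Results for two of the three aims would then be reported as PBMC expression although no step separated PBMC.

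Two things are at stake. The first is interpretation. The only bridge in the protocol from blood gene expression to muscle fatty-acid oxidation is the PBMC-to-muscle comparison in Section 3.0, and nothing similar is offered for unseparated blood. The second is analysis. Expression in a mixed sample depends on which cells are present as well as on what each cell expresses. Aim 2 works with fold changes and trajectories after the shake, and nothing planned would distinguish regulation within cells from a change in the mix.

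**Working it through.** The plan states no figure that bears directly on this, so the check is a comparison of text with two side calculations.

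**Step 1. Endpoint against workflow.** Sections 2.0, 3.0 and 4.0 require PBMC, and Aim 2 requires isolation before qPCR. The RNA, plasma and Pathology blocks and the Genetic Analysis paragraph in Section 6.0 contain no PBMC tube, no separation and no storage of cells. The documents never use the words whole blood. That reading follows from the absence of any separation step between the tube and the RNA.

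**Step 2. Could an unlisted PBMC tube fit the blood volume?** Inputs are all from Section 6.0. Per timepoint they are plasma 2.0 mL, RNA 2.5 mL, glucose and lipids 1.0 mL, insulin 2.0 mL and flush 1.0 mL. HbA1c adds 0.5 mL once. The stated maximum is 46 mL.

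- Itemised total: 5 × (2.0 + 2.5 + 1.0 + 2.0 + 1.0) + 0.5 = 5 × 8.5 + 0.5 = 43.0 mL.
- Remainder: 46 − 43.0 = 3.0 mL, or 3.0/5 = 0.6 mL per timepoint. IGF-1 and C-peptide are in the endpoint table without a listed tube and may use part of it.
- With a separate PBMC draw of 2 mL (an assumed volume) at five timepoints: 43.0 + 5 × 2 = 53.0 mL, above the maximum.

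A single baseline draw of that size would fit, but the endpoint table marks gene expression at all five times.

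**Step 3. How large could a cell-mix effect be?** Every input here is an assumption. Let m0 and m1 be the mononuclear share of the RNA-contributing cells before and after the shake. Let r be expression per mononuclear cell relative to other leukocytes. With no change of expression in any cell, the apparent fold change is

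F = (r·m1 + 1 − m1) / (r·m0 + 1 − m0).

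| Share | r = 10 | r = 2 | r = 1 | r = 0.5 | r = 0.2 |
|---|---|---|---|---|---|
| 45% to 40% | 0.911 | 0.966 | 1 | 1.032 | 1.062 |
| 45% to 35% | 0.822 | 0.931 | 1 | 1.065 | 1.125 |
| 50% to 35% | 0.755 | 0.900 | 1 | 1.100 | 1.200 |

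The extreme cells in full: (10 × 0.35 + 0.65)/(10 × 0.50 + 0.50) = 4.15/5.50 = 0.7545, and (0.2 × 0.35 + 0.65)/(0.2 × 0.50 + 0.50) = 0.72/0.60 = 1.20. These are falls in the share. For a rise of the same size the reciprocals apply: 1/1.20 = 0.83 to 1/0.7545 = 1.33.

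**Step 4. When does this reach the fitness association?** Treat the artefact as multiplicative, so that for child i the log measured change equals the log true change plus log F_i. If F is the same for every child, it moves the average trajectory and leaves the slope on fitness alone. The slope is biased by the regression of log F_i on fitness given the named covariates, and that is zero unless the shift varies with fitness after adjustment.

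**The case against.** The strongest reply concerns consequence, since no text reconciles the two descriptions.

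- A reader might infer that the PBMC endpoint cannot be measured at all. The visible text does not prove that. The tube list is not complete (IGF-1 and C-peptide have no tube), and the sample-collection figures are not available here. What stands is that no isolation step is described, and that the remaining 3.0 mL gives no sign of one at five timepoints.
- A reader might infer that changes in cell mix will be mistaken for gene regulation. The documents do not show that the mix changes within 180 minutes, by how much, or in relation to fitness. Differences between lean and overweight children are partly covered by adjustment for BMI percentile. The supportable word is can.
- A reader might take a mononuclear-only gene and a share falling from 40% to 25%, which gives 0.25/0.40 = 0.625. That is the limiting case, and nothing in the protocol suggests that the beta- and omega-oxidation genes behave that way.
- PBMC are themselves a mixture, so isolation would reduce the composition problem without removing it.
- This is a pilot. The hypothesis for the primary objective is stated in terms of metabolites (acylcarnitines and dicarboxylic fatty acids), and Section 1.0 mentions gene expression without naming PBMC. Aim 1, the metabolite analyses and the glucose and insulin responses are untouched.

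These replies limit the size and reach of the point. They do not remove the contradiction or rescue the muscle rationale for the sample actually described.

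**Conclusion.** The concern holds as an internal contradiction with a limited analytical consequence. The stated endpoint is PBMC expression; the documented procedure yields expression in unseparated blood. The PBMC-to-muscle argument therefore lacks support for the gene results of Aims 2 and 3.

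Fold changes may also carry a composition component. Its size is unknown: about 0.75 to 1.20 for assumed falls of 5 to 15 points in mononuclear share with r between 0.2 and 10, and none if per-cell expression is equal. It distorts the fitness association only under the condition in Step 4. The conclusion rests on the written collection instructions being complete as regards RNA.

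**What to change.** Reconcile the sections. Rename the endpoint whole-blood mRNA in Sections 2.0, 3.0 and 4.0, and remove the inference to PBMC and skeletal muscle or justify it afresh for whole blood. If a separation procedure is in fact in use, write it into Section 6.0 with its blood volume instead.

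For the Aim 2 gene models, prespecify a sensitivity analysis. Add a few lineage-marker genes (granulocyte, lymphocyte, monocyte) to the qPCR panel, run on the RNA already extracted, and report results with and without adjustment. Children already seen can be included, which a differential count added now would not allow.

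Two things to avoid:

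- Do not condition on these markers in the primary Aim 3 mediation models. They are measured after the challenge and may themselves be affected by fitness, so adjustment could bias the mediation estimates.
- Do not switch tubes mid-study. The revision is dated August 2023 and the study is due to end in December 2023, so a switch would mix two specimen types.

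The cost is wording, a few primer sets, a weaker stated link to muscle and some precision: with three markers the adjusted models carry 4 + 3 = 7 covariates besides fitness in 50 children.

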**Sample Collection details:**

Amount blood drawn: 2.5 mL

**CRU Post-Sample Collection:**

1. Following venipuncture, invert the collection tube 10x
2. Store and transport at room temperature

**CRU Staff will transport all samples to Williamson 6 after the visit.**

**Pathology - HbA1c (2.0 mL K2 EDTA tubes)**

Collection Timepoints: baseline (pre-shake, fasting)

**Sample Collection details:**

Minimum blood drawn: 0.1 mL

Amount blood drawn: 0.5 mL \*Please use a syringe to collect this small amount of blood.

**CRU Post-Sample Collection:**

1. Following venipuncture, invert the collection tube 10x.
2. Transport specimen at room temperature.

PROTOCOL TITLE: Metabolic Response to a High-Fat Challenge in Children and Adolescents.  
CRU Staff will transport sample to Pathology Main Lab after the baseline blood draw

**Pathology – glucose and lipid panel (2.0 mL lithium heparin tubes)**

Collection Timepoints: baseline (pre-shake, fasting), 30 minutes, 60 minutes, 120 minutes, and 180 minutes

**Sample Collection details:**

Minimum blood drawn: 0.1 mL

Amount blood drawn: 1.0 mL \*Please use a syringe to collect this small amount of blood.

**CRU Post-Sample Collection:**

1. Following venipuncture, invert the collection tube 10x.
2. Transport specimen at room temperature.

CRU Staff will transport sample to Pathology Main Lab after each blood draw

**Pathology – insulin (5.0 mL SST tubes)**

Collection Timepoints: baseline (pre-shake, fasting), 30 minutes, 60 minutes, 120 minutes, and 180 minutes

**Sample Collection details:**

Minimum blood drawn: 1.0 mL

Amount blood drawn: 2.0 mL \*Please use a syringe to collect this small amount of blood.

**CRU Post-Sample Collection:**

1. Following venipuncture, invert the collection tube 10x.
2. Transport specimen at room temperature.

CRU Staff will transport sample to Pathology Main Lab after each blood draw

**Metabolomics Analysis**

Plasma untargeted metabolomics profiling will be done by the MRC2 ([www.mrc2.umich.edu](http://www.mrc2.umich.edu), Directed by [name]), which has extensive experience in production and analysis of metabolomics data. For untargeted metabolomics, samples are analyzed on an Agilent 1200

PROTOCOL TITLE: Metabolic Response to a High-Fat Challenge in Children and Adolescents. liquid chromatography/6530 quadrupole Time-of-Flight mass spectrometry system (Agilent Technologies, Inc., Santa Clara, CA USA) using the Waters Acquity HSS T3 1.8  $\mu$ m column (Waters Corporation, Milford, MA). The eluent is analyzed in both positive and negative ion mode electrospray ionization. Each participant will provide five plasma samples for metabolomics after the intake of the high-fat dietary challenge.

## **Genetic Analysis**

The study is looking for an association between a genotype or a biomarker and a specific disease or condition, but at this point it is not clear if the genetic marker has predictive value. RNA will be isolated by the Center of Molecular Epidemiology within Dartmouth College and gene expression will be quantified using PCR for genes related to beta-oxidation, omega-oxidation, and entry into the mitochondria.

